10.3. Serious Adverse Events/Suspected Adverse Reaction

An adverse event or suspected adverse reaction is considered "serious" if, in the view of either the investigator or sponsor, it results in any of the following outcomes:

- Results in death
- Results in a life threatening adverse event
- Requires in-patient hospitalization or prolongation of existing hospitalization
- Results in persistent or significant disability/incapacity or substantial disruption of the ability to conduct normal life functions
- Is a congenital anomaly/birth defect

Important medical events that may not result in death, be life threatening, or require hospitalization may be considered serious when, based on appropriate medical judgment, they may jeopardize the subject and may require medical or surgical intervention to prevent one of the outcomes listed in this definition. Examples of such medical events include allergic bronchospasm requiring intensive treatment in an emergency room or at home, blood dyscrasias or convulsions that do not result in in-patient hospitalization, or the development of drug dependency or drug abuse.

Suspected adverse reaction means any adverse event for which there is a reasonable possibility that the drug caused the adverse event. For the purposes of IND safety reporting, "reasonable possibility" means there is evidence to suggest a causal relationship between the drug and the adverse event. Suspected adverse reaction implies a lesser degree of certainty about causality than adverse reaction, which means any adverse event caused by a drug.

Unexpected adverse event or unexpected suspected adverse reaction. An adverse event or suspected adverse reaction is considered "unexpected" if it is not listed in the investigator brochure or is not listed at the specificity or severity that has been observed; or, if an investigator brochure is not required or available, is not consistent with the risk information described in the general investigational plan or elsewhere in the

current application, as amended. For example, under this definition, hepatic necrosis would be unexpected (by virtue of greater severity) if the investigator brochure referred only to elevated hepatic enzymes or hepatitis. Similarly, cerebral thromboembolism and cerebral vasculitis would be unexpected (by virtue of greater specificity) if the investigator brochure listed only cerebral vascular accidents. "Unexpected," as used in this definition, also refers to adverse events or suspected adverse reactions that are mentioned in the investigator brochure as occurring with a class of drugs or as anticipated from the pharmacological properties of the drug, but are not specifically mentioned as occurring with the particular drug under investigation.

Emergency room visits that do not result in hospitalization (ie, an overnight stay) should be evaluated for one of the other serious outcomes to determine if they qualify as SAEs.

Preplanned hospitalizations (eg, elective procedures for preexisting conditions that did not worsen) are excluded from SAE reporting.

Study endpoints (eg, mortality or major morbidity) must be reported to FDA by the Sponsor as described in the protocol and ordinarily would not be reported under paragraph (c) of the CFR § 312.32. However, if a serious and unexpected AE occurs for which there is evidence suggesting a causal relationship between the drug and the event (eg, death from anaphylaxis), the event must be reported under CFR § 312.32(c)(1)(i) as a serious and unexpected suspected adverse reaction even if it is a component of the study endpoint (eg, all-cause mortality).

The new regulations require that "study endpoints (eg, mortality or major morbidity) must be reported according to the protocol instead of as IND safety reports except when there is evidence suggesting a causal relationship between the drug and the event."

Any worsening of hematogenous SA osteomyelitis under study because of lack of therapeutic effect of any study drug (reported within study endpoints reporting time frame) is captured as an efficacy endpoint and is, therefore, excluded from SAE reporting, unless the event is considered related to the drug.

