6.1. Outcome Measures

Primary: Safety evaluations will be conducted in the children who have started treatment with ceftaroline. Assessments will include:

- AEs, SAEs, deaths, and discontinuations due to SAEs.
- Vital signs and laboratory parameters.

Secondary:

- Clinical response (the subject has been afebrile for at least 48 hours, has negative blood cultures, is clearly improving in general, is able to eat and drink, and is able to use or move the involved extremity) at the end of parenteral therapy (approximately days 5 to 14) by subject and by baseline pathogens although *S. aureus* is expected to be the predominant pathogen.
- Clinical outcome (site of infection has complete resolution of pain, swelling and warmth and the patient is able to use the affected extremity normally and is back to normal activities) at the EOT and at the one year follow up visit.

- Clinical relapse within a year of enrollment in the study or the development of a pathologic fracture.

PK:

- Concentrations of ceftaroline fosamil, ceftaroline, and ceftaroline M-1 in plasma.
- If available, concentrations of ceftaroline fosamil, ceftaroline, and ceftaroline M-1 in purulent material such as bone or subperiosteal abscess or synovial fluid.

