6.4. Data Review Committee

A Data and Safety Review Committee (DRC) will be established to review safety data on a regular basis to ensure safety of all subjects enrolled.

A DRC meeting is to be held at regular intervals to evaluate the safety of this study and other ongoing pediatric studies of ceftaroline fosamil. The role of the DRC members is to evaluate the safety of the pediatric studies on an ongoing basis in order to determine whether any undue safety concerns are observed, and thus whether the studies should be allowed to continue enrollment.

A detailed DRC charter will be prepared by the Investigator and agreed to by all DRC members before initiation of enrollment in this study. This charter will document the timing, membership, analysis content, and review procedures for each DRC meeting. Safety information will be prepared in advance of each DRC meeting. Safety analyses will include, at a minimum, summaries of study disposition and all SAEs, deaths, and discontinuations due to AEs, PCS laboratory results, and individual subject listings of selected safety data.

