10.1. Adverse Events

An AE is any untoward medical occurrence in a clinical investigation subject administered a pharmaceutical product and which does not necessarily have to have a causal relationship with this treatment. An AE can therefore be any unfavorable and unintended sign (including an abnormal laboratory finding, for example), symptom, or disease temporally associated with the use of a medicinal product, whether or not considered related to the medicinal product.

Examples of AEs are as follows:

- Changes in the general condition of the subject.
- Subjective symptoms offered by or elicited from the subject.
- Objective signs observed by the Investigator or other study personnel.
- All diseases that occur after the start of the study, including any change in severity or frequency of preexisting disease.
- All clinically relevant abnormalities in laboratory values or clinically relevant physical findings that occur during the study.

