12.4. Safety Analysis

Adverse event and serious adverse event monitoring, vital signs and laboratory tests (CBC, BUN, Creatinine, Bilirubin, Alkaline Phosphatase, AST and ALT will be obtained within 24 hours prior to enrollment and weekly during ceftaroline treatment and at the completion of ceftaroline treatment). The Alkaline Phosphatase, Bilirubin, AST/ALT results may not be available prior to enrollment of the patient.

We do not anticipate that the AST/ALT concentrations will be > 3 UNL but if they were to be this elevated, the patient subject will be dropped from the study immediately.

Safety parameters include AEs, SAEs, deaths, clinical laboratory parameters (eg, hematology parameters, chemistry parameters), and vital signs. For each safety parameter, the last assessment made before the first dose of IV study drug will be used as the baseline for all analyses.

The incidences of TEAEs, SAEs, deaths, and discontinuations due to AEs will be summarized by system organ class and preferred term according to the Medical Dictionary for Regulatory Activities by relationship to the study drug, and by severity.

Descriptive statistics of observed results and the change from baseline will be presented for clinical laboratory results, and vital signs. The incidence of PCS laboratory results will be summarized.

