12.5. Efficacy Analysis

- Clinical response by subject and by baseline pathogen at the conclusion of IV ceftaroline.
- Clinical outcome at the completion of total therapy (IV plus oral)
- Clinical outcome at one year after enrollment into study long-term follow-up.

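### Section 10.3 exempts serious worsening of the osteomyelitis from SAE reporting because efficacy is said to capture it, but that is true only for some children, and the minimum DRC package does not name such events

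*Combined protocol and SAP*

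**What the plan says.** Section 10.3 lists the usual seriousness criteria. It then says of worsening of the infection through lack of therapeutic effect that it "is captured as an efficacy endpoint and is, therefore, excluded from SAE reporting, unless the event is considered related to the drug". Just before this, the same section states: "Study endpoints (eg, mortality or major morbidity) must be reported to FDA by the Sponsor as described in the protocol". No other section describes that reporting.

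Safety is the primary objective (5.1). The primary outcome in 6.1 is "AEs, SAEs, deaths, and discontinuations due to SAEs", plus vital signs and laboratory parameters. Section 12.4 adds: "The incidences of TEAEs, SAEs, deaths, and discontinuations due to AEs will be summarized". Among its examples of AEs, 10.1 names diseases arising after study start, "including any change in severity or frequency of preexisting disease".

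On efficacy, 12.5 begins with "Clinical response by subject and by baseline pathogen at the conclusion of IV ceftaroline" and continues with clinical outcome at the end of total therapy (EOT) and at one year. Section 6.1 adds relapse or pathologic fracture within a year.

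For the DRC, the minimum content in 6.4 is "summaries of study disposition and all SAEs, deaths, and discontinuations due to AEs, PCS laboratory results, and individual subject listings of selected safety data". Section 7.10 stops the study after treatment failures in two patients.

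**The concern.** The exemption is justified by a claim about the efficacy endpoints, so it is sound only if those endpoints record the worsening. Most of them record how the child is at a visit, not what happened on the way there.

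The primary question in this single-arm trial is safety. Serious progression of the infection is the harm most specific to an antibiotic that is not working. The exemption turns on the investigator's view that the event reflects lack of effect and is not drug related. If the event then falls outside the efficacy tables as well, the report understates serious harm. The committee that advises whether enrollment continues need not be shown it.

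**Working it through.** **1. The plan's own figure.** Section 6.2 gives n = 18 for a null success rate of at most 0.50 against at least 0.80, with 80% power and a 0.05 error rate. I looked for the smallest n with a cut-off r such that P(X ≥ r | 0.50) ≤ 0.05 and P(X ≥ r | 0.80) ≥ 0.80 under the exact binomial. At n = 18, r = 13, the error rate is 0.0481 and the power 0.867. Power is 0.798 at n = 16 (r = 12) and 0.758 at n = 17 (r = 13). So 18 reproduces, and nothing below changes it.

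**2. What could capture a worsening event.** The outcomes in 6.1, 12.3 and 12.5 are status at the end of IV therapy (EOIV), at EOT and at one year; clearance of bacteremia if cultures were positive at the start; the plasma concentration target; and relapse or fracture. Relapse appears in 6.1 without a definition and has no line in 12.3 or 12.5. The EOIV response in 6.1 sets no condition on earlier deterioration.

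**3. Tracing a child who worsens seriously and later recovers.** All subjects are inpatients on IV drug, and 10.3 counts a prolonged hospital stay as serious, so the criterion does not require an extreme event.

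| Path | Efficacy result | SAE count |
|---|---|---|
| Taken off ceftaroline for insufficient effect (7.8.2) | Failure that day and at every later assessment | Not counted |
| Stays on ceftaroline, recovers by EOIV | Response | Not counted |
| Worsens on oral drug and needs IV again (7.7.1, 8.4) | Off study; failure, relapse or indeterminate, depending on how it is classed | Not counted |
| Withdrawn without being called a failure (7.8.3) | Indeterminate from then on | Not counted |
| Worsening judged drug related | As above | Counted |

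The second path is open because 7.8.2 permits discontinuation on worsening but does not require it. The off-study criteria in 7.7.1 also do not list worsening or intensive care during IV therapy. The last row rescues little: under 10.2 the causality answer is no when the event is likely to stem from the underlying disease, which will usually describe progression of the osteomyelitis.

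**4. The AE route.** Section 10.1 would accept the event as an AE, and 12.4 would then tabulate it as treatment-emergent. But 10.3 does not say that exempted worsening is still entered as an AE, and 10.5 confines collection to research-related AEs without defining the term. Section 10.5 also asks for expedited reporting of any AE that meets a seriousness criterion, which conflicts with the 10.3 exemption.

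**5. The DRC route.** None of the items in 6.4 is a failure or worsening item, and 10.4 has the DRC follow SAEs. Disposition or the selected listings might show such a child indirectly.

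**6. Scale.** The documents give no rate of serious worsening, so these figures are illustrations.

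- One child is 1/18 = 5.6 percentage points.
- Clopper-Pearson 95% intervals: 0/18, 0 to 18.5% (upper limit 1 − 0.025^(1/18)); 1/18, 0.1 to 27.3%; 2/18 = 11.1%, 1.4 to 34.7%.
- The chance that at least one of 18 children worsens seriously is 1 − (1 − q)^18. For an assumed risk q of 5%, 10% or 20%, it is 60%, 85% or 98%. This is the chance that the question arises, not the chance that an event is lost.

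**The case against.** A reader might infer that a child who worsens seriously and recovers disappears from both the safety and the efficacy results. The documents do not support that as a general statement, for these reasons:

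- Section 7.8.2 names clinical worsening as a reason for discontinuing for insufficient effect, and the resulting failure is carried forward. Later recovery does not erase it.
- Section 10.3 exempts SAE reporting and says nothing against recording an AE. The primary outcome includes all AEs, each graded for severity (10.2), so the event could appear as a severe treatment-emergent AE.
- Deaths are listed separately in 6.1, 6.4 and 12.4, and drug-related worsening remains an SAE.
- The path for a child kept on ceftaroline is narrow. Section 7.5 bars other potentially effective systemic antibacterials, so adding one during a deterioration would conflict with remaining on protocol treatment.
- Fever duration and duration of positive cultures are summarized (12.1), which may show some of these children indirectly.
- The exemption follows paragraphs about IND safety reports and may have been meant only as a rule on reporting route.
- The DRC list is a minimum, and the charter, which is not among the documents, may ask for more. Failures are also watched through 7.10 and the similar halt in 12.7 when two subjects do not improve as expected.

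All of this stands, and it narrows the point. It does not close it. The wording exempts SAE reporting as a whole, the AE route is left to the site's reading, and 7.10 does not define treatment failure. A child kept on drug who recovers need not be called a failure, so the two-failure rule need not register that child.

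**Conclusion.** The reason given for the exemption is met only when the child is discontinued for insufficient effect or when the event is counted as a relapse, an outcome that the plan neither defines nor analyzes. A child who worsens seriously, stays on ceftaroline and recovers by EOIV, or who leaves as indeterminate, is absent from the SAE count. That child can be absent from both results if the site also records no AE. A child who leaves as indeterminate would still appear in disposition, but without the reason being evident.

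Each such child moves the SAE proportion by 5.6 points. The comparison of 0/18 with 2/18 shows scale only: it assumes two events, concerns the SAE row alone, and requires that neither child was classed as a treatment failure, since two failures would stop the study. It is not evidence that events will be lost.

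I would recommend the change because it is cheap and bears on the primary objective. It falls short of something that must be fixed before the trial can be relied on, because several other provisions catch most of these children.

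**What to change.** - **10.3:** limit the exemption to expedited IND reporting. Record any worsening that meets a seriousness criterion as an SAE, flagged as disease-related lack of effect. This also removes the conflict with 10.5.
- **12.4:** tabulate SAEs with and without the flagged events.
- **6.4:** add to every DRC package a cumulative listing of treatment failures and serious disease worsening, so that the committee can see the counts on which 7.10 depends.

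One consequential line is needed. Section 7.8.1 makes a child indeterminate when an SAE leads to discontinuation and alternative antimicrobials, while 7.8.2 makes a child discontinued for insufficient effect a failure. The text should say that the new flag does not move a child from failure to indeterminate.

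The cost is a few sentences, one extra listing and an SAE count that may look slightly less favourable. Sample size, treatment, discontinuation rules and the stopping threshold are untouched.

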10.4. Follow Up of Serious Adverse Events

When additional relevant information becomes available, the investigator will record follow-up information according to the same process used for reporting the initial event as described above. The investigator will follow all SAEs until resolution, stabilization, or the event is otherwise explained. DRC will follow all SAEs until resolution, stabilization, until otherwise explained, or until the last patient completes the final follow-up, whichever occurs first.

10.5. Collecting and Reporting Adverse Events and Serious Adverse Events

Research related AEs and SAEs are collected from the signing of the informed consent form (ICF) (and assent form, if applicable) until EOT. At Month 12 follow up problems such as pathologic fractures and growth disturbances will be evaluated. The investigational site personnel are to follow unresolved AEs and SAEs at EOT until resolution or stabilization.

At each visit, subjects and/or their parent(s) (or other legally acceptable representative[s]) are to be queried regarding any new or ongoing AEs/SAEs that have occurred since the previous visit. Each, as appropriate, will be asked to volunteer information with a non-leading question such as, for the subjects, "How have you felt since your last visit?" Study center personnel will then record all pertinent information on the appropriate screens of the subject's eCRF.

All research related AEs/SAEs reported by the subject or subject's parent(s) (or legally acceptable representative[s]) or observed or otherwise identified by the Investigator (or other study site personnel) at a defined study visit or during any communication with the subject (or subject's representative[s]) occurring outside a defined study visit must be documented.

All research related AEs must be recorded on the appropriate CRF, whether or not they are considered causally related to the study drug.

For every AE, the Investigator must:

- Provide an assessment of the severity, causal relationship to the study drug), and seriousness of the event (ie, SAE).
- Document all actions taken with regard to the study drug.
- Detail any other treatment measures taken for the AE.

Within 24 business hours of learning of any AE that meets one of the criteria for an SAE, the study center personnel must report the event to Allergan on an SAE/AESI form (Global Patient Safety & Epidemiology Form) and to the FDA and IRB per regulation/local IRB policy.

If, during follow-up, any nonserious AE worsens and eventually meets the criteria for an SAE, that AE should be recorded as a new SAE.

The PI will transmit the SAE/AESI Form to the email and fax number indicated on the most current version of the form. Even if an initial report is made by telephone, an SAE/AESI form completed with all available details must still be emailed/faxed within 24 business hours of knowledge of the event at the study center.

Supplemental information shall be submitted as soon as available and may include laboratory results, radiology reports, progress notes, hospital admission and emergency room notes, holding and observation notes, discharge summaries, autopsy reports, and death certificates.

The Investigator is expected to take all therapeutic measures necessary for resolution of the SAE/AE. Any medications or procedures necessary for treatment of the SAE/AE must be recorded on the appropriate screen(s) of the subject's CRF. All SAEs/AEs are to be followed until resolution or until the SAE/AE is deemed stable. The Sponsor may contact the study center to solicit additional information or follow up on the event.

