- o Record the findings of a complete physical examination including physical findings of hematogenous SA osteomyelitis (eg, warmth, tenderness, swelling, erythema, and movement of the infected extremity). Involved extremity will be assessed as at enrollment, if possible. Most of the subjects are expected to have surgical incision and drainage procedures and thus assessing the extremity for swelling, erythema, warmth and tenderness may not be possible because of drains in place and large surgical dressings that cannot be removed.
- o Record height and weight.
- o Record vital signs: resting pulse, blood pressure, and respiratory rate; and highest daily temperature (Tmax) measured.
- o Identify, assess, and record any AEs and SAEs starting from the time that informed consent is obtained.
- o Record adjunctive therapeutic procedures (eg, surgeries).

Laboratory Assessments (assessments will be performed for research unless they are already being performed per standard of care; exceptions are indicated)

- o Any protocol-required eligibility laboratory evaluations already done locally as part of the subject's regular medical care within 24 hours before the start of the first dose of IV study drug do not have to be repeated for purposes of this study.
- o Collect complete blood count (CBC) with differential and CRP, ESR, BUN, and Creatinine lab results.
- o Blood cultures per standard of care.
- o Obtain blood samples for Alkaline Phosphatase, Bilirubin, AST and ALT.
- o Obtain blood sample for Direct Coombs test.
- o Obtain urine sample for pregnancy test (for a female who has reached menarche); ensure that the test is negative before enrollment.
- o Estimate CrCl using the updated Schwartz "bedside" formula (Schwartz et al, 2009):
$$\text{CrCl (mL/min/1.73m}^2\text{)} = \frac{0.413 \times \text{height (length) (cm)}}{\text{serum creatinine (mg/dL)}}$$
- o Collect purulent material from bone only if a procedure is performed for standard of care.

- Enroll subject after verifying that the subject meets all study inclusion and no exclusion criteria. There

should be no medically inappropriate delay in enrollment and subsequent administration of IV study drug.

9.2. Study Day 1

- Study Drug Administration:

IV ceftaroline fosamil **15 mg/kg** (or 600 mg if > 40 kg) infused over 120 (\pm 10) minutes q8h (\pm 1 hour) for children **2 years of age – 17 years** of age (inclusive).

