IV ceftaroline fosamil **10 mg/kg** infused over 120 (\pm 10) minutes q 8h (\pm 1 hour) for children from **1 year of age to < 2 years** (inclusive).

The following Clinical and Laboratory Assessments for Study Day 1 do not need to be repeated if dosing of study medicine is done on the same day as the baseline visit:

- Clinical Assessments - after at least 1 dose of IV study drug (assessments will be performed for research unless they are already being performed per standard of care; exceptions are indicated):
 - o Record concomitant medications (Section 8.3). For subjects who are being breast fed, record all medications taken by the lactating mother.
 - o Record resting vital signs (pulse, blood pressure, and respiratory rate), and highest postdose temperature measured.
 - o Record adjunctive therapeutic procedures (eg, surgeries).
 - o Record standard of care radiology results.
 - o Evaluate and record physical findings of hematogenous SA osteomyelitis (eg, warmth, tenderness, swelling, erythema, and movement of the infected extremity). Most of the subjects are expected to have surgical incision and drainage procedures and thus assessing the extremity for swelling, erythema, warmth and tenderness may not be possible because of drains in place and large surgical dressings that cannot be removed. The degree of the subject's ability to ambulate will be assessed if the osteomyelitis is in the lower extremity-i.e. walks unaided, able to bear weight, can walk aid using a walker, etc. The use of upper and lower extremities will be assessed in terms of movement and range of motion.
 - o Identify, assess, and record any new or ongoing AEs or SAEs
- Laboratory Assessments - after at least 1 dose of IV study drug (assessments will be performed for research unless they are already being performed per standard of care; exceptions are indicated)
 - o If clinically indicated, calculate CrCl using the updated Schwartz "bedside" formula (Schwartz et al, 2009).
 - o Collect results of blood cultures only if conducted per standard of care.
 - o Collect purulent material from bone only if a procedure is performed for standard of care.

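### Section 10.5 limits adverse-event recording to undefined research-related events, in conflict with the visit instructions to record any event; the wording risks under-counting in the primary safety data

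*Combined protocol and SAP*

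**What the plan says.** Section 10.5 uses the term *research related* three times, without defining it there or elsewhere:

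- Collection, from consent to end of therapy (EOT): "Research related AEs and SAEs are collected from the signing of the informed consent form".
- Documentation: the events that must be documented, whether reported by the family or identified by site staff, carry the same qualifier.
- CRF entry: "All research related AEs must be recorded on the appropriate CRF, whether or not they are considered causally related to the study drug".

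Other text in Section 10.5 is unrestricted. At each visit families are to be "queried regarding any new or ongoing AEs/SAEs that have occurred since the previous visit". The list of investigator assessments applies to every AE, and expedited SAE reporting applies to any AE that meets a seriousness criterion.

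The visit procedures in Section 9 carry no qualifier. Baseline (9.1) says "Identify, assess, and record any AEs and SAEs starting from the time that informed consent is obtained". Day 1, Days 2-14, end of IV treatment (EOIV), Weeks 2/4/6 and EOT (9.2 to 9.6) say "Identify, assess, and record any new or ongoing AEs or SAEs".

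Section 10.1 is neutral on cause: "An AE is any untoward medical occurrence in a clinical investigation subject administered a pharmaceutical product", "which does not necessarily have to have a causal relationship with this treatment". Section 12.4 plans that "The incidences of TEAEs, SAEs, deaths, and discontinuations due to AEs will be summarized", with relationship to study drug as one of the tabulation factors. Safety at the end of IV therapy is the primary objective (5.1) and endpoint (12.2). Section 6.1 lists AEs and SAEs, unqualified, among the primary outcome measures.

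**The concern.** The section that governs AE collection appears to ask for a judgement on attribution before an event reaches the database. Section 12.4 needs the opposite order: record everything, then classify by relationship.

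The order matters here because the study is open-label and single-arm, enrols 18 children, and expects most of them to have surgical drainage (9.1). In such patients many events have a competing explanation, and there is no control group against which to check an attribution. If the site leaves an event off the CRF because it seems due to the operation or the infection, the safety analysis never sees it. The recorded TEAE incidence can only fall as a result, and the related/unrelated split loses events mainly from its unrelated side.

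**Working it through.** No stated figure bears on AE capture. The sample size of 18 in Section 6.2 rests on a single-stage binomial calculation that does not use AE rates, so it is unaffected. The check is a comparison of texts, followed by one illustration based on an assumption.

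**Step 1. Which instructions conflict?**

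| Section | Function | Scope |
|---|---|---|
| 9.1-9.6 | What staff record at each visit, consent to EOT | Any AE or SAE |
| 10.5, three sentences | What is collected, documented, entered on the CRF | *Research related* only |
| 10.5, remaining text | Eliciting, assessing, SAE reporting | Any or every AE |
| 10.1 | What an AE is | Any cause |
| 10.2 | Yes/No causality for the study drug | Presupposes that unrelated events are recorded |
| 12.4 | TEAE incidence, by relationship | All TEAEs |

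The direct conflict is between 10.5 and 9.1-9.6, because both set recording scope over the same window. Section 10.1 defines an AE and does not itself say what must be collected, so it clashes with 10.5 only if the qualifier is read as a filter on attribution.

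**Step 2. What could the qualifier mean?**

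- *Related to the study drug.* Excluded. The CRF sentence in 10.5 says that these events are recorded whether or not the drug caused them. If the two terms meant the same, that clause would be empty.
- *Occurring during study participation.* Harmless, but redundant: the first sentence already sets the window from consent to EOT.
- *Arising from the research rather than from standard of care.* Plausible. Section 9 repeatedly contrasts assessments done for research with those done as standard of care, and 6.3 labels the oral treatment standard of care. A coordinator could on this reading omit events blamed on surgery, the infection or the oral antibiotic. The causality clause does not bring them back, because it applies only to events already classed as *research related*.

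Section 10.2 shows what the third reading would lose. Its grounds for answering No include attribution to underlying or concurrent disease and to other drugs. The form therefore expects to hold the very events that this reading would leave out.

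**Step 3. Which results are exposed?**

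Vital signs and laboratory results (6.1, 12.4) do not pass through the three sentences. The SAE reporting duty in 10.5 is unqualified. The exposure is therefore mainly non-serious clinical AEs. For the primary endpoint, fixed at the end of IV therapy, the relevant omissions would be events attributed to surgery or the infection. Oral treatment starts only after the EOIV assessments (9.4), so omissions blamed on oral drugs would affect the wider TEAE summary up to EOT.

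**Step 4. Illustration only.**

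Let p be an event's true per-child incidence and k the share of such events that pass the filter. The documents do not give k, so 0.25 to 1 is assumed. Take p = 5%, the order of the eosinophilia rate quoted in 4.3, used only as a scale. The chance of recording at least one case in 18 children is 1 − (1 − pk)^18:

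- k = 1: 1 − 0.95^18 = 60.3%
- k = 0.75: 1 − 0.9625^18 = 49.7%
- k = 0.5: 1 − 0.975^18 = 36.6%
- k = 0.25: 1 − 0.9875^18 = 20.3%

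These figures show how the result depends on k. They do not estimate the loss in this trial.

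**The case against.** The strongest reply is that the protocol as a whole does require full capture. Section 9 is what staff follow visit by visit, and it says to record any AE or SAE across the whole window. Section 10.5 itself asks families about any event and requires severity, causality and seriousness for every AE. On this view the two words are loose drafting that a trained site would ignore. Much of this stands: it rules out saying that the trial limits AE collection to a subset, and it makes under-recording a possibility rather than a fact. It does not remove the defect. Section 10.5 is the dedicated section on AE collection, it repeats the qualifier three times, and nothing says which section prevails.

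Two stronger readings are tempting, and the documents support neither.

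- A reader might equate *research related* with drug related and apply this to the adolescent study in 4.2.3, where 8 TEAEs occurred in 5 of 9 subjects and 3 events in 3 subjects were judged related. That would suggest 5 of 8 events unrecorded (62.5%) and incidence falling from 5/9 (55.6%) to 3/9 (33.3%). The arithmetic is right, but the CRF sentence in 10.5 excludes the premise, so this is not even a valid worst case.
- A reader might infer that an SAE such as that study's unrelated pathologic fracture would be lost. The SAE reporting duty has no such qualifier, and pathologic fracture is also captured as a secondary outcome (6.1) and at the Month 12 visit (9.7, 10.5).

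**Conclusion.** The point holds as an internal inconsistency with a possible effect on the primary safety data. Section 10.5 restricts AE recording by an undefined term, while 9.1-9.6 require any AE to be recorded and 10.1, 10.2 and 12.4 assume that this was done.

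The consequence is conditional. If staff apply the qualifier as a filter on attribution, non-serious AEs are missed, the TEAE incidence is biased downward, and the analysis cannot put the events back. If staff follow Section 9, nothing is lost. The documents give no basis for the size of any loss, and the percentages for k below 1 rest on an assumed share. TEAE incidence is one component of the primary safety endpoint, not the whole of it. The sample size and its error rates do not change.

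The correction is worth making because the exposed result is primary, the loss could not be corrected in analysis, and the remedy is close to free.

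**What to change.** Delete *research related* in all three places in Section 10.5, so that every AE and SAE meeting the 10.1 definition is collected, documented and entered on the CRF from consent to EOT, as 9.1-9.6 already direct. Keep relationship to study drug as the Yes/No assessment in 10.2 and as a tabulation factor in 12.4, made after the event is recorded.

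If children have already been enrolled under the present wording, the report should state how the site applied the term.

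The cost is a change of wording plus some additional AE entries in 18 children. No sample size, visit or assessment changes.
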